# 1.0 Introduction

Post liver transplant maintenance immunosuppression is based on calcineurin inhibitors, which have a nephrotoxic effect. Calcineurin inhibitors cause microvascular and glomerular damage and are associated with arteriolar hyalinosis and striped interstitial fibrosis of the kidneys. Early calcineurin inhibitor related changes may be reversible but nephrotoxicity with chronic administration of these immunosuppressant agents appears to be irreversible and can sometimes lead to renal transplantation. Significant renal impairment has been observed in 27% of liver transplant recipients at 5 years postoperatively, with up to 10% reaching end stage renal disease. Such late chronic renal failure has been associated with a significant risk of premature death and can be predicted by creatinine levels in the first year post liver transplant. With the implementation of the MELD (Model for End Stage Liver Disease) liver allocation system, more patients are reaching liver transplantation with baseline renal dysfunction as creatinine is heavily weighted within the MELD score.

Everolimus is a macrolide immunosuppressant of the proliferation signal inhibitor class (PSI, mTOR inhibitor). It is an orally active 40-O-(2-hydroxyethyl) derivative of sirolimus, which blocks growth factor-dependent cellular proliferation through a calcium independent signal. The immunosuppressive effect of everolimus is exerted by blocking interleukin 2 and interleukin 15 driven proliferation of hematopoietic (T & B cells) and non hematopoietic (vascular smooth muscle cells) cells by inhibiting the activation of p70S6 kinase. This arrests the cell cycle at the G1 phase thus preventing the progression into the S phase. Both everolimus exerts its inhibitory effect by forming a complex with the immunophilin FK506 binding protein 12. The 50% inhibitory concentration for everolimus inhibition of FK506 binding to FK506 binding to FK506 binding protein 12 is 1.8 to 2.6 nmol/L which is approximately 3x higher than that of sirolimus (0.4-0.9 nmol/L).

Interest in mTOR inhibitors, such as everolimus, lies in their potential renal sparing effect in the setting of calcineurin inhibitor maintenance therapy in heart, renal and liver transplantation. Everolimus as the newer of the mTOR inhibitor agents has the advantage of a shorter half life (40 hrs), allowing a once daily oral administration. Data showing improvement of renal function when an mTOR inhibitor completely replaces a calcineurin inhibitor in renal transplantation makes such a strategy particularly attractive as a renal sparing immunosuppressive regimen for liver transplant recipients.

A high proportion of liver transplant candidates on the Penn State Hershey Medical Center waiting list are in renal failure at the time of liver transplant. From September 2005 until January 2011, a total of 111 orthotopic liver transplants were performed. Forty three (39%) of these recipients showed evidence of renal failure in the pre- transplant period with a creatinine level > 2mg/dL. Fifteen patients required intra-operative continuous venovenous hemodiafiltration (CVVHD), 8 required CVVHD pre-transplant and five underwent dialysis in the post transplant period. The predominant cause of renal failure in these patients was hepatorenal syndrome with a prolonged course in some patients due to the long waiting time and organ donor shortage. The postoperative immunosuppressive protocol implemented at Penn State consists of a combination of a calcineurin inhibitor (tacrolimus or cyclosporine), mycophenolic acid and steroids (tapered over the first 3 months).

Given the increasing proportion of patients having renal failure at the time of transplant, associated with the nephrotoxic effect of calcineurin inhibitor based immunosuppression associated with its long term negative survival impact, this study proposes to examine the renal sparing impact of conversion to everolimus from a calcineurin inhibitor based immunosuppressive protocol between 90 days -120 days post liver transplant. 90 days-120 days post transplant was chosen to allow for the switch to everolimus to occur at a period of stable post transplant liver function when both technical and rejection risks are lower. The 90 days-120 days was also chosen because of data indicating that worsening renal function at 4 weeks, 3 months and 1 year post transplant is an independent risk factor for the development of chronic renal failure and end stage renal disease after orthotopic liver transplantation.

IRB # 38115 Version: December 28, 2018

# 2.0 Objectives

#### Primary:

Examine the renal sparing impact of implementing a strategy of conversion to everolimus from a calcineurin inhibitor based immunosuppressive protocol between 90 days-120 days post liver transplant.

Secondary:

- Evaluate patient and liver graft survival at 6, 12, and 24 months.
- Evaluate incidence and severity of biopsy proven rejection at 6, 12, and 24 months.
- Evaluate the cost-effectiveness of the strategy of conversion to everolimus from calcineurin inhibitor between 90 days-120 days post liver transplant.
- Perform recipient and donor genotyping to examine their impact on optimizing the dosage of everolimus.

# 3.0 Study Design and Methods

- This is a prospective randomized open label pilot study to assess superiority of immunosuppressive regimen. Patients will be randomized to one of two arms between 90 days-120 days post transplant:
- **Arm A:** Conversion to Everolimus immunosuppression combined with mycophenolic acid (Myfortic: MPA), and complete discontinuation of Calcineurin inhibitor will occur after the target level of Everolimus is reached.
- **Arm B:** Continuation with standard immunosuppressive therapy consisting of Calcineurin inhibitor associated with mycophenolic acid (Myfortic: MPA).
- Steroids are routinely discontinued at 3 months post transplant as part of the Penn State standard immunosuppressive protocol (Exceptions to steroid discontinuation: Primary diagnosis of autoimmune cirrhosis, primary biliary cirrhosis and primary sclerosing cholangitis).
- Recipients of a deceased donor liver transplant who are 18-70 years of age will be asked between 90 days -120 days post transplant whether they wish to participate in this study.

-

# 4.0 Inclusion and Exclusion Criteria

Study Population: This will be a pilot study which will include 12 adult deceased donor liver transplant recipients in each study arm.

#### Inclusion

• Ability and willingness to provide written informed consent and adhere to study regimen.

Amendment 6Page 4 of 18

IRB # 38115

Version: December 28, 2018

- Recipients who are 18-70 years of age of a primary liver transplant from a deceased donor.
- Allograft is functioning at an acceptable level by the time of randomization as defined by the AST, ALT, Total Bilirubin levels ≤3 times ULN, and AlkP and GGT levels ≤ 5 times ULN. Elevated GGT alone, in combination with AST, ALT, total bilirubin and AlkP within the defined range does not exclude patients from randomization.
- Recipients who have been initiated on an immunosuppressive regimen that contains corticosteroids and tacrolimus or cyclosporine by 7 days post-transplantation.
- Confirmed recipient HCV status at Screening (either by serology or by PCR). Laboratory results obtained within 12 months of screening are acceptable.
- Abbreviated MDRD eGFR ≥ 30 mL/min/1.73m2. Local and central serum creatinine results obtained within 5 days prior to randomization are acceptable, however no sooner than Day 25 post-transplantation.
- Verification of at least one tacrolimus trough level of ≥ 8 ng/mL in the week prior to randomization. Investigators should make adjustments in tacrolimus dosing to continue to target trough levels above 8 ng/mL prior to randomization.
- Patients who are able to take oral medication at time of randomization.

### Exclusion

- Patients who are recipients of multiple solid organ or islet cell tissue transplants, or have previously received an organ or tissue transplant. Patients who have a combined liver kidney transplant.
- Recipients of a liver from a living donor, or of a split liver.
- History of malignancy of any organ system within the past 5 years whether or not there is evidence of local recurrence or metastases, other than non-metastatic basal or squamous cell carcinoma of the skin or HCC (see next criteria).
- Hepatocellular carcinoma that does not fulfill Milan criteria (1 nodule ≤ 5 cm, 2-3 nodules all < 3 cm, seen at the time of transplantation as per explant histology of the recipient liver.
- Any use of antibody induction therapy.
- Patients with a known hypersensitivity to the drugs used on study or their class, or to any of the excipients.
- Patients who are recipients of ABO incompatible transplant grafts.
- Recipients of organs from donors who test positive for Hepatitis B surface antigen or HIV are excluded.
- Patients who have any surgical or medical condition, which in the opinion of the investigator, might significantly alter the absorption, distribution, metabolism and excretion of study drug.
- Women of child-bearing potential (WOCBP), defined as all women physiologically capable of becoming pregnant, including women whose career, lifestyle, or sexual orientation precludes intercourse with a male partner and women whose partners have been sterilized by vasectomy or other means, UNLESS (1) they meet the following definition of post-menopausal: 12 months of natural (spontaneous) amenorrhea or 6 months of spontaneous amenorrhea with serum FSH levels >40 mIU/m, or (2) have past 6 weeks from surgical bilateral oophorectomy with or without hysterectomy or (3) are using one or more of the following acceptable methods of contraception: surgical sterilization (e.g., bilateral tubal ligation, vasectomy), hormonal contraception (implantable, patch, oral), copper coated IUD and double-barrier methods ( any double combination of male or female condom with spermicidal gel, diaphragm, sponge, cervical cap). Periodic abstinence (e.g., calendar, ovulation, symptothermal, post-ovulation methods) and withdrawal are not acceptable methods of contraception. Reliable contraception should be maintained throughout and for 3 months after study drug discontinuation.

• Patients with any history of coagulopathy or medical condition requiring long-term anticoagulation which would preclude liver biopsy after transplantation. (Low dose aspirin treatment or interruption of chronic anticoagulant is allowed).

#### **Enrollment Exclusion - Randomization**

- Patients who have severe hypercholesterolemia (>350 mg/dL; >9 mmol/L) or hypertriglyceridemia (>500 mg/dL; >8.5 mmol/L) within 6 months of transplantation. Patients with controlled hyperlipidemia are acceptable at the time of randomization.
- Patients with platelet count < 50,000/mm3 at the time of randomization.
- Patients with an absolute neutrophil count of < 1,000/mm^3 or white blood cell count of <2,000/mm^3 at the time of randomization.
- Patients who have tested positive for HIV. Negative laboratory results obtained within 6 months prior to transplant are acceptable.
- Patients with clinically significant systemic infection requiring active use of IV antibiotics at the time of randomization. Patients who are in a critical care setting at the time of randomization requiring life support measures such as mechanical ventilation, dialysis, requirement of vasopressor agents.
- Patients who require renal replacement therapy for clearance within 7 days prior to randomization.
- The presence of thrombosis via Doppler ultrasound of the major hepatic arteries, major hepatic veins, portal vein and inferior vena cava. Results obtained within 5 days prior to randomization are acceptable, however no sooner than Day 25 post-transplantation.
- An episode of acute rejection that required antibody therapy or more than one steroid sensitive episode of acute rejection during the run-in period. This includes patients who have not completed steroid treatment for acute rejection within 7 days prior to randomization.
- Patients with a confirmed spot urine protein-to-creatinine ratio that indicates greater than 0.7 mg protein /mg creatinine. Laboratory results obtained after transplant surgery and within 4 months of randomization are acceptable.
- Use of immunosuppressive agents or treatments after baseline that are not utilized in the protocol.

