### Protocol

Version: December 28, 2018

Randomization will only occur between 90days and 120 days post transplant. Patients randomized between 90 days and 120 days for conversion to Everolimus, in association with Mycophenolic acid, will start Everolimus at a dose of 0.75mg twice daily, with target levels at 3 to 8 ng/mL. Blood levels of Everolimus will be measured by the FDA approved assay by ThermoFisher. The calcineurin inhibitor (tacrolimus or cyclosporine) will be withdrawn after the target levels of Everolimus are reached.Concurrent immunosuppression with MPA will be maintained in both arms with dosage dependant on the degree of bone marrow suppression and leucopenia.

The calcineurin inhibitor (tacrolimus or cyclosporine) will be withdrawn after the target level of Everolimus is reached.

For Tacrolimus: After everolimus blood trough levels have been confirmed to be in the target range (3-8 ng/mL), tacrolimus tapering will begin, targeting a tacrolimus whole blood trough level of 3-5 ng/mL by three weeks after randomization. Once that point is reached tacrolimus elimination will begin while maintaining everolimus whole blood trough levels within the target range of 6-8 ng/mL.

For Cyclosporine: After everolimus blood trough levels have been confirmed to be in the target range (3-8 ng/mL), cyclosporine tapering will begin, targeting a cyclosporine whole blood trough level of 50 to 100 ng/mL by three weeks after randomization. Once that point is reached cyclosporine elimination will begin while maintaining everolimus whole blood trough levels within the target range of 6-8 ng/mL.

Prior to CNI elimination, the inclusion criteria for liver function tests will be re-applied. If a patient does not exhibit a functioning allograft at an acceptable level by as defined by the AST, ALT, Total Bilirubin levels being ≤3 times the upper limits of the normal values (ULN) and Alkaline Phosphatase and Gamma Glutamyl Transferase levels ≤5 times ULN, then the patient will be monitored until these criteria are met, after which tacrolimus/cyclosporine elimination can begin.

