#### Side effects of lothalamate clearance test:

Rare allergic reactions to iothalamate in subjects known to be allergic to iodine. Can range from urticaria to anaphylactic shock. Other adverse effects of iothalamate include arrythmias, bradycardia, generalized vasodilation, extravasation of iothalamate during injection, seizures, and weakness of extremities. Abnormal sensation or muscle spasm in the injection site has been reported but in patients being infused with five to thirteen times the amount planned in this study and at a faster infusion rate.

Mycophenolic acid has bone marrow suppression as the main side effect and rarely may have neurotoxicity associated with it. It is also an enteric coated formulation and hence should have less of the GI side effects such as nausea, vomiting and diarrhea, than mycophenolic mofetil which is a similar drug.

Given that arm A will consist of the patients on everolimus and mycophenolic acid, with complete withdrawal of calcineurin inhibitor, there will be a risk of bone marrow suppression and leucopenia, which will be dosage dependent.

Both calcineurin inhibitors and mycophenolic acid increase the patient risk for cancer, especially post transplant lymphoproliferative disease. Everolimus is thought to have an antiproliferative effect and may reduce the risk for the development of cancer.

All patients will be monitored closely for any of the above side effects. Other than the scheduled study clinic visits and testing, allpatients will be followed as per the Penn State Division of Transplantation follow up guidelines. For the first 24 months post liver transplant all our patients undergo the following routine lab collection procedure, the frequency of which may be adjusted based on patient clinical status and need:

Routine/standard of care laboratory tests from post op month 1 through post op month 24 include: :

✓ 1st 5 months postop: 2x/week labs as follows: Sodium, Potassium, Chloride, Bicarbonate level, BUN, Creatinine, Magnesium, Calcium, Phosphorus, CBC, PT, INR, PTT, Liver Function Tests (Total & Direct Bilirubin, AST, ALT, Alkaline Phosphatase & Gamma Glutamyl Transferase), Glucose & Immunosuppressive agent trough levels. Lipid Panel to be performed once a week.

PRAMS00038115 Approval: 1/7/2020

IRB # 38115

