# Protocol

If everolimus is interrupted for safety reasons for longer than 21 consecutive days, or for more than 2 episodes of 7 days or longer, discontinuation of study medication will be maintained and the patient will be removed from the study.

During the course of the trial everolimus will be administered on a b.i.d. regimen. Everolimus will not be provided to patients after they have discontinued the study.

If reduction of everolimus is necessary for the patient to remain in target trough range, everolimus dosing will be reduced by 0.25 mg intervals.

In cases of hyperlipidemia, lipid lowering therapy will be optimized before dosage reduction of study medication is considered. Patients will be managed with HMG Co-A reductase inhibitors (e.g., fluvastatin). Lovastatin or simvastatin will not be utilized. The starting dose of HMG Co-A reductase inhibitors will be equivalent to 20 mg pravastatin or 20 mg fluvastatin, and may be increased to target with the aim of maintaining a LDL level of < 130 mg/dL. Patients will be monitored for the development of rhabdomyolysis or other adverse events.

Both everolimus and mycophenolic acid have a bone marrow suppressant effect and predispose patients to neutropenia. Patients who develop neutropenia with an absolute neutrophil count (ANC) <1000 will be initially treated with administration of neupogen (filgrastim) at a dose of 5mcg/kg/day subcutaneously prior to dose reduction of immunosuppressant agents. If there is no response to neupogen therapy after 3 consecutive treatment days, dose reduction of mycophenolic acid, a dose reduction in everolimus should be undertaken as outlined below.

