#### Guidelines for everolimus dose reduction/interruption:

	Platelet count (/mm3)	Hemoglobin (g/dL)	ANC count (K/UI)	Cholesterol (mmol/L)	Triglycerides (mmol/L)
Dose reduction	≤ 75,000	≤ 8	≤ 1000	≥ 8	≥ 6.5
Interruption	≤ 50,000	≤ 6	≤ 500	≥9	≥ 8.5

All patients will be carefully assessed for any of the side effects or adverse reactions related to everolimus through a detailed history and physical examination during clinic visits as listed above and through a thorough and complete examination of their routine and study laboratory values.

A foley catheter placement is required during iothalomate testing to accurately measure urine output collection. Risks of foley catheter placement include: pain, hematuria, injury to urethra, urinary retention following removal of foley, urinary tract infection and bladder spasms.

Patients will be withdrawn from the study in the event of a serious life threatening adverse event.

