#### **Monitoring Process:**

Primary monitoring of the study will be performed by the study team, who will review accrual, adverse events, and dose limiting toxicities on a real-time basis. Cumulative adverse events and study toxicities will be reviewed weekly. The study team will make decisions regarding dose escalation, cessation of accrual, and whether stopping rules have been reached. A Data Safety Monitoring Board (DSMB) has been created and its members are listed in the study protocol at the end of Section 13. The DSMB will review the study progress reports provided to the DSMB by the study team and a statistician. A DSMB report will be generated by the DSMB and forwarded to the IRB and the PI. A copy of any interim DSMB reports will be included with continuing review reports submitted by the PI for IRB review.

If stopping rules have been reached, this will be communicated to the IRB immediately.

Serious adverse events that would qualify for patient removal from study would include:

- Refractory leucopenia ≤ 500 unresponsive to drug dose reduction/interruption or stimulation by Neupogen (filgrastim).
- Persistant thrombocytopenia at <50,000/mm3, unresponsive to study medication dose reduction/interruption.
- Refractory hyperlipidemia (Cholesterol ≥ 9 mmol/L or Triglycerides ≥ 8.5 mmol/L ) unresponsive to treatment (as outlined in section 7 of the protocol) and to study medication dose reduction/interruption.
- Refractory anemia (Hemoglobin ≤ 6 g/dL) not related to surgical bleeding, and unresponsive to blood transfusion and to study medication dose reduction/interruption.
- Development of hemolytic uremic syndrome
- Development of any thrombotic events such as liver graft hepatic arterial or portal/hepatic venous thrombosis, or thrombotic microangiopathy or thrombotic thrombocytopenic purpura, or radiologically documented pulmonary embolism.
- Refractory seizures or neurologic side effects unresponsive to treatment or reduction/interruption of study medication.
- Life threatening infectious complications.

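### The triglyceride exclusion prints 500 mg/dL and 8.5 mmol/L as one limit, but they differ by about half, and the plan does not say which governs

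*Combined protocol and SAP*

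**What the plan says.** Section 4.0, under Enrollment Exclusion - Randomization, bars patients with severe hypercholesterolemia (>350 mg/dL; >9 mmol/L) or "hypertriglyceridemia (>500 mg/dL; >8.5 mmol/L) within 6 months of transplantation". The next sentence adds a carve-out: "Patients with controlled hyperlipidemia are acceptable at the time of randomization". Controlled is not given a numeric definition.

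Elsewhere, triglyceride limits appear in SI units only. In Section 7.0, the table of everolimus dose reduction and interruption has a column whose heading begins "Triglycerides (mmol/L"; it sets reduction at 6.5 or above and interruption at 8.5 or above. Section 10.0, under Monitoring Process, lists refractory hyperlipidemia, including "Triglycerides ≥ 8.5 mmol/L", as a reason for removal. Conventional units are also used for lipids: the statin guidance in Section 7.0 aims at "maintaining a LDL level of < 130 mg/dL". The documents do not state which unit is used at screening or which of the two exclusion figures takes precedence.

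**The concern.** Printing a limit in two units with a semicolon between them tells site staff that either figure may be used. That is safe only if the two figures are the same quantity. Here they are not, so the answer to whether a given patient may be randomized can depend on the unit in which the result is read.

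What is at stake is limited. Hyperlipidemia that counts as controlled is acceptable at randomization under either figure, so only patients in the disputed band whose triglycerides are not controlled are affected. Still, this is an operative eligibility rule for a drug that the plan itself associates with hypertriglyceridemia, and a rule of this kind should give one answer.

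**Working it through.** **Inputs from the documents.** Triglyceride exclusion: 500 mg/dL and 8.5 mmol/L. Cholesterol exclusion in the same sentence: 350 mg/dL and 9 mmol/L. Both are in Section 4.0.

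**Assumption.** The documents give no conversion factors. I take 88.57 mg/dL per mmol/L for triglycerides, with a range of 85 to 90, and 38.67 for cholesterol, with a range of 38 to 39. The formula is mg/dL = mmol/L × factor.

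**Step 1: try to reproduce the printed pair.** The factor implied by the pair is 500 / 8.5 = 58.8, well outside 85 to 90. Applying the cholesterol factor by mistake does not reproduce it either: 8.5 × 38.67 = 329 mg/dL, and 500 / 38.67 = 12.9 mmol/L.

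**Step 2: convert each triglyceride figure.**

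| Factor (mg/dL per mmol/L) | 500 mg/dL in mmol/L | 8.5 mmol/L in mg/dL | Ratio to 500 |
|---|---|---|---|
| 85 | 5.88 | 723 | 1.45 |
| 88.57 | 5.65 | 753 | 1.51 |
| 90 | 5.56 | 765 | 1.53 |

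The gap is 723 − 500 = 223 to 765 − 500 = 265 mg/dL. Rounding cannot explain it.

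**Step 3: check the method on the cholesterol pair.** 9 × 38.67 = 348 mg/dL against the printed 350; over the range 38 to 39 the result is 342 to 351. That pair is consistent, so the format is meant as an equivalence and only the triglyceride pair fails.

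**Step 4: apply the rule as written.** A value above 500 mg/dL and up to about 750 mg/dL is excluded by the first figure and admitted by the second. If either figure is enough to exclude, the working limit is 500 mg/dL. If the SI figure is used alone, it is about 750 mg/dL.

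**Step 5: check the two possible repairs.** 500 / 5.6 = 89.3 and 750 / 8.5 = 88.2. Both fall within 85 to 90, so either would be a consistent pair.

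**The case against.** The strongest reply is that the criterion already works in practice: if a patient is excluded on meeting either printed figure, the limit is 500 mg/dL. In addition, the carve-out for controlled hyperlipidemia leaves much of the band to the investigator's judgement. Both points stand and keep the matter small. Neither makes the pair correct, and the plan does not state the either-figure rule.

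A second reply is that 500 mg/dL may be the misprint. The figure 8.5 mmol/L recurs as the interruption and removal level, and the cholesterol and platelet exclusions (9 mmol/L; 50,000/mm3) sit at their own interruption levels. Against that, the neutrophil exclusion (1,000/mm3) sits at the dose-reduction level, so the pattern is not conclusive. This reply also stands in part: the documents do not show which figure was intended, and a reader who infers that 500 mg/dL must be the right one goes too far.

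Two further inferences are tempting and should not be drawn.

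- A reader might infer a distinct safety harm: under 8.5 mmol/L, a patient could start everolimus already at or above the 6.5 mmol/L dose-reduction level. The plan's self-consistent limits allow the same thing. Cholesterol up to 9 mmol/L is admitted although reduction begins at 8, and platelets from 50,000/mm3 are admitted although reduction begins at 75,000. It is a general feature of these criteria, not a consequence of the unit error. Moreover, "lipid lowering therapy will be optimized before dosage reduction of study medication is considered".
- A reader might infer from the planned study dates in Section 6.0 that enrolment had closed before this version of December 28, 2018. Those dates are only planned, and page footers carry an approval of 1/7/2020, after the planned end of 1 October 2019. The documents do not establish when enrolment ended.

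**Conclusion.** The point holds as a minor error. The two triglyceride figures differ by a factor of 1.45 to 1.53, the plan does not reconcile them, and eligibility of patients with uncontrolled values between about 500 and 750 mg/dL depends on which is applied. The conclusion rests on an assumed factor of 85 to 90 mg/dL per mmol/L; the printed pair would need 58.8.

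The consequence is confined to who may enter. The criterion applies before randomization and to both arms alike, so it creates no between-arm bias. It does not enter the primary comparison of creatinine clearance or the sample size. The documents do not say how many of the 24 planned patients fall in the band, and the number may be zero.

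**What to change.** Replace the pair with one consistent limit. The default should be >500 mg/dL (>5.6 mmol/L): it is the stricter printed figure and the limit that results if either figure excludes. If the sponsor confirms that 8.5 mmol/L was intended, keep that figure and change the mg/dL value to about 750.

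If patients have already been randomized, report which limit was applied and how many had an available triglyceride value between about 500 and 750 mg/dL. Say that coverage is incomplete. The routine panels listed in Section 7.0 begin at postoperative month 1, with "the frequency of which may be adjusted based on patient clinical status and need", and Section 6.0 states: "Randomization will only occur between 90days and 120 days post transplant". Those panels can therefore cover at most the first 90 to 120 days after transplant before a patient is randomized. The criterion also leaves open whether its six months run before transplant, after it, or both.

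The cost is one line of wording and, if needed, one line in the report with a check of lipid values already on file. The default has one small downside: possibly fewer eligible patients.
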